4.1 Overall Design

We will determine the feasibility of conducting a randomized controlled trial of tight blood pressure control (<135/85 mmHg on home BP monitoring) vs. standard of care (<150/100 mmHg on home BP monitoring) in postpartum individuals following a HDP with assessment of individuals who are eligible, enrolled, and remain in the study until six weeks postpartum. We will further assess individuals who are retained in the study for 6 months postpartum. Lastly, we will analyze our effect outcomes to inform the sample size for a subsequent large-scale randomized trial. This will be done through analysis of mean arterial pressure (MAP), systolic

blood pressure, and diastolic blood pressure of participants at 6 weeks and at 6 months postpartum.

The study will be conducted on the postpartum unit of Magee-Womens Hospital. Participants will be enrolled at the time of postpartum hospitalization with study visit #1 occurring in the hospital. At this study visit, participants will be administered questionnaires, will provide a blood sample, and BP will be measured. Study visit #2 will be a remote study visit conducted via telemedicine or a telephone call at 6 weeks postpartum. At this visit, participants will provide questionnaires and blood pressure data. Study visit #3 will be a remote study visit conducted via telemedicine or a telephone call at 6 months postpartum. At this visit, participants will again provide questionnaires and blood pressure data. The study overview is depicted below.

4.2 Scientific Rationale for Study Design

Our central hypothesis is that conducting a single-site RCT of tighter control (<135/85 mmHg in the outpatient setting) of postpartum BP during the first six months postpartum will be feasible. Secondly, tighter control will lead to lower blood pressure and improved cardiac remodeling. These findings will translate longer-term to a reduced risk of chronic hypertension and cardiovascular disease, an important, understudied condition in women with significant morbidity.

4.3 Justification for Dose

The current blood pressure thresholds for anti-hypertensive medication initiation for all adults as per ACC/AHA, except pregnant and postpartum individuals is 140/90 mmHg in the clinic or 135/85 mmHg at home. Accordingly, a threshold of 135/85 for home blood pressure values was selected.

4.4 End of Study Definition

The study will be concluded following assessment of blood pressure and questionnaires at study visit #3, which occurs 6 months postpartum.

5 Study Population

5.1 Inclusion Criteria

Postpartum individuals ≥ 18 years old with preeclampsia or gestational hypertension diagnosed by ACOG criteria and enrolled in our Connected Care remote monitoring program.

5.2 Exclusion Criteria

Fetal anomaly, pre-pregnancy hypertension, diabetes, cardiac, or chronic kidney disease.

5.3 Strategies for Recruitment and Retention

Recruitment: We will recruit 60 individuals with preeclampsia or gestational hypertension from the MWH postpartum units, using recruitment methods effectively employed by our team previously. There are approximately 100 eligible individuals per month (~1200 per year).

We plan to recruit women from the post-delivery unit with the appropriate diagnoses. Upon review of a potential subject's chart to determine eligibility, the study coordinator will flag the chart for potential eligibility. The potential participant will first be approached by the study physician or a member of the clinical care team directly caring for her to ask about her willingness to be approached for participation in a research study. If the potential participant indicated willingness to be approached, then the research team will be contacted and the potential subject will be screened regarding enrollment.

Retention: Participants will receive monetary compensation which will be distributed amongst their study visits. We propose monetary compensation of \$125 total with \$25 distributed at enrollment, \$25 distributed at the first study visit, and \$25 distributed at the second study visit and \$50 at the final study visit.

Randomization and blinding: We will randomize consented participants into two arms: tight BP control (<135/85 mmHg) vs. usual care in 1:1 at the individual level. A randomization sequence using permuted block randomization with randomly varying block sizes will be generated by RedCap. This will be a pragmatic, non-masked trial. At randomization, treating physicians will be notified of their patient's participation and randomization group.

6 Study Intervention

6.1 Study Intervention(s) Administration

6.1.1 Study Intervention Description

Following hospital discharge, individuals with HDP are enrolled in a clinical home BP management program and are prompted, via a secure text message to report their BP for the first six weeks postpartum. This program is overseen by Drs. [name] and [name]. Remote monitoring nurses will be unblinded to treatment arm and will follow study protocols for enrolled participants based on study arm.

6.1.2 Dosing and Administration

Treatment group: Participants in the active arm will be initiated on oral anti-hypertensive therapy if their blood pressure is persistently elevated defined as ≥ 2 measures more than 4 hours apart that are greater than or equal to 135/85 mmHg with titration to maintain BP <135/85 mmHg on home blood pressure monitoring. As this is a pragmatic trial, we will not mandate the use of a specific anti-hypertensive agent, rather will leave the choice of the agent to clinical decision making.

Usual care: Usual care in this period includes initiation of oral anti-hypertensive therapy if blood pressure is persistently elevated defined as ≥ 2 measures more than 4 hours apart that are greater than or equal to $\geq 150/100$ mmHg with titration to maintain BP <150/100 mmHg on home blood pressure monitoring.

6.3 Measures to Minimize Bias: Randomization and Blinding

We will randomize consented participants into two arms: tight BP control (<140/90mmHg) vs. usual care in 1:1 at the individual level. A randomization sequence using permuted block randomization with randomly varying block sizes will be generated by RedCap. We will use a permuted block randomization scheme with random block sizes in order to ensure balance within each block of participants and to preserve allocation concealment. This will be a pragmatic, non-masked trial. At randomization, treating physicians will be notified of their patient's participation and randomization group.

6.3 Study Intervention Compliance

Adherence to the study protocols through the clinical remote monitoring program will be monitored by the study team. Adherence to medication will be assessed at each study visit. Adherence to home BP monitoring will be assessed throughout the study period.

7 Study Intervention Discontinuation and Participant Discontinuation/Withdrawal

7.1 Discontinuation of Study Intervention

7.2 Participant Discontinuation/Withdrawal from the Study

An investigator may discontinue or withdraw a participant from the study for the following reasons:

- If any clinical adverse event (AE), laboratory abnormality, or other medical condition or situation occurs such that continued participation in the study would not be in the best interest of the participant
- If the participant meets an exclusion criterion (either newly developed or not previously recognized) that precludes further study participation

The reason for participant discontinuation or withdrawal from the study will be recorded. Subjects who sign the informed consent form and are randomized but do not receive the study intervention may be replaced. Subjects who sign the informed consent form, and are randomized

and receive the study intervention, and subsequently withdraw, or are withdrawn or discontinued from the study will not be replaced.

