7.3 Lost to Follow-Up

A participant will be considered lost to follow-up if they fail to return for any scheduled visit.

The following actions will be taken if a participant fails to return to the clinic for a required study visit:

- The study team will attempt to contact the participant and reschedule the missed visit and counsel the participant on the importance of maintaining the assigned visit schedule and ascertain if the participant wishes to and/or should continue in the study.
- Before a participant is deemed lost to follow-up, the investigator or designee will make every effort to regain contact with the participant (at least 3 telephone calls and / or text messages)

8 Study Assessments and Procedures

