Secondary outcomes are systolic and diastolic BP, and chronic hypertension at 1-year postpartum (stage 1 or stage 2) derived from office BP in women randomized to tight control compared to women to receiving usual care. We will also compare the use of anti-hypertensive agents across the study period, quantitatively assessed using the therapeutic intensity score [TIS], which is a summary measure that accounts for the number of medications and the relative doses received, which will be summarized across the study period and compared by randomization arm. As an exploratory analysis, we will quantitatively simulate BP based on confounding effects of anti-hypertensive medications using published metrics of the lowering effect of various anti-hypertensive agents. Finally, we will evaluate care utilization across study arms, including postpartum readmission and Emergency Room visits

Questionnaires: The participant will complete questionnaires about demographics, medical history, obstetric and gynecologic history, physical activity, mood, diet, breastfeeding, sleep, and overall health and support. At subsequent visits, the participant will also answer questions about the intervention.

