8.2 Safety and Other Assessments

Answering Questionnaires: There is a possibility of emotional discomfort associated with answering the questionnaire as some of the questions may be considered “personal” and answering them might be stressful or embarrassing. Participants may skip questions for which they feel uncomfortable.

Risks of the Tight Control Intervention Program: For some women, there may be a small but present risk of hypotension, meaning your blood pressure goes too low. If this occurs, it may cause symptoms such as dizziness, shortness of breath, palpitations, light-headedness, and/or falls. We advise women who are experiencing these symptoms to immediately contact their health-care provider and to avoid carrying their newborn due to risk of falls. Additionally, we will monitor rates of breastfeeding continuation given the theoretical risk for decreased milk supply.

9 Statistical Considerations

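### Section 7.2 lets an unmasked investigator withdraw a randomized woman from the whole study, not only from her BP target, and no visible text keeps her in the remote follow-up contacts

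*Combined protocol and SAP*

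**What the plan says.** Section 7.2 introduces its rule with "An investigator may discontinue or withdraw a participant from the study for the following reasons". Two reasons follow. The first is an adverse event, laboratory abnormality or other condition, limited to cases where "continued participation in the study would not be in the best interest of the participant". The second reads "If the participant meets an exclusion criterion (either newly developed or not previously recognized) that precludes further study participation". Both are permissions rather than requirements, and both carry a limit. The reason for leaving is to be recorded. Of women who consent, are randomized "and receive the study intervention, and subsequently withdraw, or are withdrawn or discontinued from the study will not be replaced", so the sample does not make good the loss.

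Other sections bear on the rule:

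- Section 6.3 (randomization and blinding): the trial is not masked, and treating physicians are told the arm.
- Sections 1.1 and 4.1: the tight target lasts 6 weeks. The 6-week and 6-month visits are held remotely and collect BP and questionnaires.
- Section 7.3: when a woman misses a visit, "the investigator or designee will make every effort to regain contact with the participant".
- Section 8.1: "At subsequent visits, the participant will also answer questions about the intervention".
- Section 8.2: "we will monitor rates of breastfeeding continuation given the theoretical risk for decreased milk supply".
- Section 6.3 (compliance): "Adherence to medication will be assessed at each study visit". Section 9.4.2 reports the share of women still on their assigned treatment and, separately, the reasons for attrition.
- Section 9.3: every analysis is by intention to treat.

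**The concern.** An adverse event or a late-found exclusion can be a sound reason to stop managing a woman to a study BP target. It is rarely a reason to stop telephoning her. Section 7.2 makes the study, not the target, the thing she leaves.

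The decision is a judgment that can be made knowing the arm, and the reasons may be tied to arm or outcome. Symptomatic hypotension is a named risk (section 2.3.1), and section 8.2 links hypotension to tight control, so adverse-event withdrawals could gather in that arm. The exclusions in section 5.2 include pre-pregnancy hypertension, cardiac disease and chronic kidney disease. It is my inference, not the plan's statement, that persistently high postpartum BP could prompt one of these diagnoses. If so, the second reason would select on the outcome after randomization. The direction of any bias is unknown.

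A woman withdrawn in this way contributes no later visit MAP, no later answers about the intervention and no later breastfeeding status. If she left because of an adverse event, she is likely to have had harm to report. She also counts against retention alongside women who refused or could not be reached, and section 9.4.2 uses retention to size the next trial. If the rule passes into that larger trial, selective loss will not shrink with sample size as the standard error does.

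**Working it through.** **Inputs from the plan.** 60 randomized, 30 per arm; MAP standard deviation (SD) 8 mmHg; target difference 5 mmHg; 80% retention, so 48 women or 24 per arm; type I error 20%; 80% power (section 9.2). Retention to 6 months and acceptability each have a target above 80% of randomized participants (section 8.1 table).

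**Assumed.** The documents give no expected number of investigator withdrawals. I take k = 1 to 3 of 30 in one arm, with MAP differing from the rest of that arm by d = 8 to 16 mmHg (1 to 2 SDs), in either direction.

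**1. The plan's own figures.** The standard error of the arm difference at 24 per arm is 8 × √(2/24) = 2.31 mmHg. Two-sided power at 20% is Φ(5/2.31 − 1.28) = 0.81 (0.807 with the t distribution), which matches the stated 80%. The within-arm margin of error is 1.96 × √(0.25/30) = 0.179, which matches 0.18. The point does not depend on an error in either figure.

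**2. The text side by side.** Section 7.3 tries to recover women who miss a visit. Sections 6.3 (compliance) and 9.4.2 treat staying on assigned treatment as distinct from attrition, so women off target are probably followed in general. Neither provision reaches a woman whom the investigator has withdrawn from the study under 7.2.

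**3. Shift in an arm's mean MAP if those women are missing: k × d / 30.**

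| k | d = 8 | d = 16 |
|---|---|---|
| 1 | 0.27 mmHg | 0.53 mmHg |
| 3 | 0.80 mmHg | 1.60 mmHg |

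Against 2.31 mmHg this is 0.27/2.31 = 0.12 to 1.60/2.31 = 0.69 of a standard error. If nobody else is lost and k = 3, the standard error is 8 × √(1/30 + 1/27) = 2.12 mmHg, still above 1.60. The largest shift is 1.60/5 = 32% of the target difference.

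**4. Power.** If the withdrawals come on top of the planned 20% loss and all fall in one arm, power goes from 0.812 to 0.805, 0.798 and 0.791 for k = 1, 2 and 3. This is a minor cost.

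**5. Retention.** One to three withdrawals take off 1/60 = 1.7 to 3/60 = 5.0 points overall, and 1/30 = 3.3 to 3/30 = 10.0 points in that arm. The 95% half-widths at 80% are 1.96 × √(0.16/60) = 10.1 points overall and 1.96 × √(0.16/30) = 14.3 points within an arm. Since 48/60 = 80.0% misses a target above 80% and 49/60 = 81.7% meets it, 11 losses are allowed.

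**6. Acceptability.** Suppose 24 of 30 women in an arm find the intervention acceptable. On the plan's denominator, randomized participants, the result is 24/30 = 80.0% whether or not some of the other 6 go unsurveyed. Only with a denominator of surveyed women, which the plan does not state, would it read 24/29 = 82.8% to 24/27 = 88.9%.

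**The case against.** The strongest reply is that 7.2, read strictly, already does most of what is wanted. Withdrawal is optional. An adverse event counts only if staying in the study is against the woman's interest, and an exclusion only if it rules out further participation. A remote contact would seldom meet either test. Leaving the target does not need 7.2 at all, since the trial is pragmatic and 9.4.2 tracks women who leave assigned treatment. This stands as a limit on how often the rule should be used. It does not settle what happens once the rule is used, because what she leaves is still the study.

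Several further points stand:

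- The event or condition that prompts withdrawal is recorded, and earlier data are kept. Withdrawal after the 6-week visit leaves the powered MAP outcome intact.
- Utilization comes from the hospital system (section 3) and home BP from the clinical program (section 6.1.1), so both may be retrievable, though the plan does not say so. Standardized visit MAP and questionnaire answers would not be.
- Recorded reasons already allow investigator withdrawals to be separated from refusal and lost contact when retention is reported.
- Criterion-based cases should be rare. Charts are reviewed for eligibility before approach (section 5.3), and few of the listed exclusions can arise after delivery.
- Section 7.1, where a rule for stopping the target but staying in follow-up would naturally sit, shows no text in the copy reviewed. I draw nothing from that. If the full document has such a rule, 7.2 needs only to be aligned with it.

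A reader might infer that any adverse event removes a woman, or that all her outcome, harm and acceptability data are lost. The limiting wording and the retained data do not support either reading.

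**Conclusion.** The concern holds in a limited form. As written, 7.2 permits selective loss after randomization that sits badly with the intention-to-treat statement in 9.3, and no visible text keeps the affected women in the 6-week and 6-month contacts. What is at risk is visit MAP, questionnaire answers and breastfeeding status due after withdrawal.

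The number of cases is unknown and probably small. For the assumed 1 to 3 women in one arm, the effects on MAP and retention lie within the pilot's sampling error, and acceptability does not move on the plan's own denominator. A reader might infer a demonstrated bias in the MAP comparison or an inflated acceptability result. The documents support neither: they give no count of withdrawals, no direction and no difference in MAP, and section 9.4.1 puts estimation ahead of testing. The case for changing the text is that the change costs little, makes the stated analysis principle achievable, and avoids carrying the rule into a larger trial.

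**What to change.** State in 7.2 that the two investigator reasons end only management to the study BP target, with care then decided clinically. Keep the woman in the planned remote BP and questionnaire contacts at 6 weeks and 6 months and in utilization capture, and analyse her in her randomized arm. End follow-up only when she withdraws consent or, rarely, when contact itself is not in her interest, and record which applied. Report stopping of the BP target and its reasons by arm, separately from retention.

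The cost is a few sentences. The contacts are already planned for every randomized woman, and utilization is already to be drawn from the hospital system. The drawback is slight dilution of the effect estimate by women no longer on their assigned target, which intention to treat already implies.

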7.3 Lost to Follow-Up

A participant will be considered lost to follow-up if they fail to return for any scheduled visit.

The following actions will be taken if a participant fails to return to the clinic for a required study visit:

- The study team will attempt to contact the participant and reschedule the missed visit and counsel the participant on the importance of maintaining the assigned visit schedule and ascertain if the participant wishes to and/or should continue in the study.
- Before a participant is deemed lost to follow-up, the investigator or designee will make every effort to regain contact with the participant (at least 3 telephone calls and / or text messages)

8 Study Assessments and Procedures

8.1 Efficacy Assessments

Feasibility outcomes: As listed in Table, will include enrollment, randomization, retention.

Blood pressure measurement: Mean arterial pressure (mmHg) at six weeks and six months postpartum will be assessed at a remote research study visit. MAP is defined as the average BP during one cardiac cycle and will be calculated

as $MAP = SBP + 2(DBP)/3$. BP will be measured in all women in a standardized manner by trained research staff using the same validated device as at the enrollment visit. Due to diurnal variations in BP, we will attempt to schedule all study visits between 8-10am consistent with clinical guidelines. If this cannot be performed due to participant scheduling limitations, we will ensure that BP is measured at a consistent time of the day across all visits. Following a 5-minute rest, BP will be measured in triplicate on the non-dominant arm with one-minute intervals using an appropriately sized cuff. These measures will be directly observed by research study staff.

Table. Feasibility outcomes		
Feasibility outcome	Descriptive statistic	Feasibility target
Identification of participants	mean, SD, 95% CI	Review 50 medical records per month to assess for eligibility
Screening	mean, SD, 95% CI	Average screening rate of 8-10 participants/month
Enrollment	mean, SD, 95% CI	Average enrollment rate of 4-5 participants/month
Randomization	n, %, 95% CI	>80% of enrolled participants
Retention to 6 months postpartum	n, %, 95% CI	>80% of randomized participants
Study measures consistency	n, %, 95% CI	>90% of randomized participants
Acceptability	n, %, 95% CI	>80% of randomized participants based on survey questionnaires

Secondary outcomes are systolic and diastolic BP, and chronic hypertension at 1-year postpartum (stage 1 or stage 2) derived from office BP in women randomized to tight control compared to women to receiving usual care. We will also compare the use of anti-hypertensive agents across the study period, quantitatively assessed using the therapeutic intensity score [TIS], which is a summary measure that accounts for the number of medications and the relative doses received, which will be summarized across the study period and compared by randomization arm. As an exploratory analysis, we will quantitatively simulate BP based on confounding effects of anti-hypertensive medications using published metrics of the lowering effect of various anti-hypertensive agents. Finally, we will evaluate care utilization across study arms, including postpartum readmission and Emergency Room visits

Questionnaires: The participant will complete questionnaires about demographics, medical history, obstetric and gynecologic history, physical activity, mood, diet, breastfeeding, sleep, and overall health and support. At subsequent visits, the participant will also answer questions about the intervention.

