2.3.3 Assessment of Potential Risks and Benefits

3 Objectives and Endpoints

OBJECTIVES	ENDPOINTS	JUSTIFICATION FOR ENDPOINTS
Primary		
	
Is a randomized controlled trial of tight blood pressure control (<135/85 mmHg on home blood pressure monitoring) vs. standard of care (<150/100 mmHg on home blood pressure monitoring) in postpartum individuals following a hypertensive disorder of pregnancy (HDP) feasible?
 
We hypothesize that average enrollment will represent 10 participants per month, greater than 80% of enrolled participants will undergo randomization, and six-month retention will represent greater than 80% of randomized patients.
	
The outcome measures will determine whether a large-scale randomized controlled trial is feasible at our institution.

Secondary		
	
Does randomization to tight blood pressure control (<135/85 mmHg on home blood pressure monitoring) following a hypertensive disorder of pregnancy result in lower mean arterial pressure (MAP) at 6 weeks and 6 months postpartum to inform the sample size for a large-scale randomized trial?
 
We hypothesize that among women randomized to tight blood pressure control, there will be lower mean arterial blood pressures (MAP) at 6 months postpartum and can ascertain the sample size for a large-scale randomized trial accordingly.
 
Does randomization to tight blood pressure control (<135/85 mmHg on home blood pressure monitoring) following a hypertensive disorder of pregnancy result in lower diastolic
	
Mean arterial pressure (MAP): Importantly, MAP accounts for both systolic and diastolic BP, and weights diastolic BP more strongly. While most hypertension trials in older adults employ systolic BP as the primary outcome, our preliminary data supports the importance of isolated diastolic hypertension in young women, particularly following a hypertensive disorder of pregnancy.
 
Systolic blood pressure and diastolic blood pressure are surrogate values for diagnosis of elevated blood pressure at 6 weeks and 6 months postpartum.

OBJECTIVES	ENDPOINTS	JUSTIFICATION FOR ENDPOINTS

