9.2 Sample Size Determination

We will focus on the 60 randomized participants. While the sample size may appear to be limited, the goal of the pilot is to collect information for planning a larger efficacy study. Our sample size is based on the confidence interval for our feasibility measures as outlined above. Assuming 30 participants within each study group and a 5% type I error rate, we will have the ability to estimate within-arm 95% confidence interval margin-of-errors of no more than 0.18 for each of our feasibility outcomes. For our efficacy outcomes, in our prior work, mean MAP at 6 weeks postpartum following a HDP was 94 (SD 8) mmHg. Although the primary objective of this pilot trial is obtaining information on feasibility and acceptability used to inform design of a confirmatory trial, we will perform a preliminary test for efficacy to confirm that this line of research warrants further study. Assuming a study retention of 80% (n=48 individuals, which we exceeded in our pilot work) and a 20% type I error rate, we will have 80% power to detect a difference of 5 mmHg in mean MAP at visit 2. Because this is a pilot study designed to test feasibility outcomes, we are using a higher than 5% type 1 error rate for the efficacy analysis because any “positive” finding in our pilot will be followed by a confirmatory efficacy trial.

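### The MAP formula printed in section 8.1 divides only the diastolic term by 3, so it does not give mean arterial pressure; the planning figures are unaffected, but the formula needs correcting

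*Combined protocol and SAP*

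**What the plan says.** Section 8.1, under blood pressure measurement, first describes the quantity in words: "MAP is defined as the average BP during one cardiac cycle and will be calculated". The sentence then completes the calculation "as $MAP = SBP + 2(DBP)/3". No other section gives a formula for MAP.

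Two other places show what the quantity is meant to be:

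- The endpoint justification in section 3 (Objectives and Endpoints table) prefers MAP to systolic pressure because "MAP accounts for both systolic and diastolic BP, and weights diastolic BP more strongly". It ties this to isolated diastolic hypertension in young women.
- Section 9.2 plans on prior work in which "mean MAP at 6 weeks postpartum following a HDP was 94 (SD 8) mmHg". With 48 participants retained and "a 20% type I error rate", it states that "we will have 80% power to detect a difference of 5 mmHg in mean MAP at visit 2".

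Section 9.4.3 makes MAP at 6 weeks and 6 months the comparison of interest between arms. Sections 3 and 4.1 say that the blood pressure results are to inform the sample size of a larger trial.

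**The concern.** MAP is the only efficacy outcome with a power statement, and section 8.1 is the only place that says how to derive it. As printed, the rule is SBP + (2/3) x DBP. That is not an average over the cardiac cycle, and it favours systolic pressure when the stated reason for choosing MAP is that it favours diastolic.

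An analyst who follows the rule as printed would produce values that cannot be compared with the planning mean and SD. The mean, SD and between-arm difference at both visits would be on another scale. Those are the figures that the pilot exists to hand on to the next trial.

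**Working it through.** **Inputs from the documents.** The formula in 8.1; planning mean 94 and SD 8 (9.2); difference 5 mmHg, alpha 0.20 and 48 analysed (9.2); 1:1 allocation (5.3), hence 24 per arm.

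**Step 1: reproduce the plan's own figure.** Standard error of the difference = 8 x sqrt(2/24) = 2.309. Standardised difference = 5/2.309 = 2.165. For two-sided alpha 0.20 the critical value is 1.282, so power = Phi(2.165 - 1.282) = Phi(0.883) = 0.81 (0.807 with the t distribution). This agrees with the stated 80%. A one-sided test would give 0.91, so the plan's figure is two-sided.

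**Step 2: evaluate the two forms.**

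| BP (mmHg) | As printed: SBP + 2 x DBP/3 | Bracketed: (SBP + 2 x DBP)/3 |
|---|---|---|
| 120/80 | 173.3 | 93.3 |
| 122/80 | 175.3 | 94.0 |
| 135/85 | 191.7 | 101.7 |
| 150/100 | 216.7 | 116.7 |

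**Step 3: compare with the protocol's own statements.**

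- *Definition in 8.1.* An average over the cardiac cycle must lie between diastolic and systolic pressure. The printed form adds two thirds of DBP to SBP, so it always exceeds SBP.
- *Rationale in section 3.* The printed weights are 1 on SBP and 0.67 on DBP, so systolic counts 1.5 times as much as diastolic. The bracketed weights are 1/3 and 2/3, so diastolic counts twice as much as systolic.
- *Planning mean in 9.2.* A printed-form value of 94 at SBP 120 would need DBP = (94 - 120) x 1.5 = -39. More generally, a mean of 94 would need a mean SBP below 94. The bracketed form gives 94.0 at 122/80.

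**Step 4: effect on the SD (illustration only).** The documents give no SDs for SBP and DBP at 6 weeks and no correlation. Assume SDs of 10 and 8 and a correlation of 0.7:

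- As printed: sqrt(100 + (4/9) x 64 + (4/3) x 0.7 x 10 x 8) = sqrt(203.1) = 14.3.
- Bracketed: sqrt(100 + 4 x 64 + 4 x 0.7 x 10 x 8)/3 = sqrt(580)/3 = 8.0.

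Over SBP SD 10 to 14, DBP SD 8 to 10 and correlation 0.5 to 0.8, the SD is about 13.5 to 19.7 as printed and 7.6 to 10.8 bracketed.

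**Step 5: what that does to power depends on the effect.** Use SDs 14.3 and 8.0, 24 per arm and two-sided alpha 0.20.

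- *Equal fall of 5 mmHg in SBP and DBP.* The printed difference is 5 + (2/3) x 5 = 8.3 and power is about 77%. The bracketed difference is 5 and power is about 81%.
- *Fall of 7.5 mmHg in DBP alone.* The difference is (2/3) x 7.5 = 5 on both scales. Power is about 47% as printed and 81% bracketed.

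**The case against.** The strongest case on the other side is that this is an obvious missing bracket with no effect on the design. Much of that stands.

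- The wording of 8.1, the rationale in section 3 and the planning mean leave little doubt about what was meant. The stated power reproduces.
- MAP values above a participant's own systolic pressure would be conspicuous, and MAP can be recomputed from the recorded SBP and DBP without loss of data.
- MAP is a secondary outcome in a 60-person feasibility pilot. Section 9.4.1 says that hypothesis testing is not the main aim, and the feasibility outcomes are untouched.
- The text was read from PDF, so an outer bracket or stacked fraction could have been lost. The inner brackets and the slash survived, which makes a source error more likely but does not prove it.

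Several stronger readings are tempting, and the documents do not support them:

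- *That the trial is underpowered or sized on the wrong scale.* Step 1 shows otherwise.
- *That the diastolic signal would be lost.* Diastolic pressure is a separate endpoint at both visits.
- *That the mean of 94 fits only one formula.* It rules out the printed form, but another MAP convention, DBP + 0.4 x (SBP - DBP), gives 78 + 0.4 x 40 = 94 at 118/78.
- *That the SD of 8 by itself identifies the formula, or that a particular loss of power follows.* Both rest on assumed SDs and correlation, and the power loss also on the assumed split of the effect between SBP and DBP.

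What the objection does not remove is that the protocol's only derivation rule for this outcome gives wrong values if followed.

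**Conclusion.** The formula in 8.1 is wrong as it stands in the text reviewed. The contradictions with the definition in 8.1, the rationale in section 3 and the planning mean in 9.2 need no outside figure. At 120/80 the printed form overstates MAP by 173.3 - 93.3 = 80 mmHg, and it reverses the intended order of the weights.

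Sample size and stated power do not change. Harm arises only if the formula is programmed as printed. The size of any loss of power is then uncertain: with the assumed SDs and correlation it runs from about 4 percentage points (equal systolic and diastolic effect) to about 34 (diastolic effect only). A mean and SD passed to the next trial on this scale would be misleading in either case.

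This is a minor but necessary correction. It rests on the printed page agreeing with the extracted text, which the sponsor can settle at once.

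**What to change.** 1. Check the original page of section 8.1 to confirm that the bracket is missing there.
2. If it is, replace the formula with MAP = (SBP + 2 x DBP)/3.
3. Verify that form wherever MAP is derived, whether in data capture or in analysis code. The documents mention RedCap only for generating the randomization sequence, so the place of derivation has to be identified first.
4. As a standing check, confirm that every derived MAP lies between that participant's DBP and SBP.

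The cost is one line of text and a short programming check. No change to sample size, visits or data collection follows.
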